RE-DEFINE:

Refugee Emergency: DEFining and Implementing Novel Evidence-based psychosocial interventions

Study protocol for review by WHO Ethical Review Committee.

Turkey

11 March 2019

Version 4.1

Contact person:

[name], PhD

World Health Organization (WHO)

Department of Mental Health and Substance Abuse

Email: [contact]

[contact]

PROJECT SUMMARY

Background

Since the start of the war in Syria in 2011, more than 5 million Syrians had to take refuge in a safer place and they had chosen neighbouring countries including Turkey, Lebanon, Jordan, Iraq and countries in Africa including Egypt and North Africa (1). Along with displacement from their homes, refugees also have been susceptible to countless traumatic events and lack of vital needs during and after displacement (2). Physical and mental challenges they endure do not end after resettlement as well. As a consequence of aforementioned adversities, refugees are at great risk of developing symptoms of common mental disorders, notably posttraumatic stress disorder (PTSD), depression, anxiety and related somatic health symptoms along with other forms of disabling psychological distress (3;4;5;6;7). The World Health Organization (WHO) has developed a new low-intensity 5session self-help intervention called Self-Help Plus (SH+) in order to manage stress and cope with adversity (8). SH+ is a brief and trans-diagnostic intervention which may be delivered by trained non-specialists facilitators to people with and without mental disorders. SH+ has been evaluated in RCTs in low and middle income countries, while there is no rigorous evidence on its cost-effectiveness in preventing the onset of mental disorders in refugees in Turkey.

Objectives

To evaluate the effectiveness and cost-effectiveness of SH+ in Arabic speaking people including Syrians under the temporary protection of Republic of Turkey and other Arabic speaking immigrants and asylum seekers with psychological distress resettled in Turkey, as compared with enhanced treatment as usual (ETAU). The primary outcome is the reduction in the incidence of any mental disorders. Secondary outcomes are mental health symptoms, psychological functioning, well-being, drop-out rates, and economic outcomes.

Design

This is a parallel-group randomized controlled trial, in which participants will have an equal probability (1:1) of being randomly allocated to the SH+ intervention or the ETAU.

Methodology

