The World Health Organization (WHO) has developed a new low-intensity 5-session selfhelp intervention called Self-Help Plus (SH+) in order to manage stress and cope with adversity such as chronic poverty, displacement, gender-based violence and long-term armed conflict (8). SH+ is a brief and trans-diagnostic (i.e., addresses depressed mood, posttraumatic stress, other stress reactions and client-defined psychosocial problems) intervention which may be delivered by trained non-specialists facilitators to people with and without mental disorders. This intervention does not only aim to help people in coping with adversity but also increasing their psychological functioning and well-being. Small pilot studies without a control group have been conducted in order to investigate feasibleness of SH+ with South Sudanese refugees in Northern Uganda and Syrian people in Syria and South Turkey. The aims of the studies were to investigate feasibility and acceptability of the programme and to identify any further adaptations required prior to further effectiveness testing in a large cluster randomized controlled trial (recently successfully completed with positive results in Uganda). Against this background, this study will test the effectiveness of SH+ in reducing the incidence of common mental disorders (i.e. depression, anxiety, PTSD) and improving psychological functioning, mental health symptoms among Arabic speaking people including Syrians under the temporary protection of Republic of Turkey and other Arabic speaking immigrants and asylum seekers resettled in Turkey. Also, this study will evaluate the cost-effectiveness of SH+ in Turkey.

STUDY GOALS AND OBJECTIVES

Objectives

The objective of this parallel-group randomized controlled trial is to evaluate the effectiveness and cost-effectiveness of SH+ in refugees with psychological distress resettled in Turkey, as compared with enhanced treatment as usual (ETAU). The primary objective is testing the effectiveness of SH+ in reducing the incidence of any mental disorders. Secondary objectives are the evaluation of mental health symptoms, psychological functioning, well-being, drop-out rates, and economic outcomes.

Study hypotheses

- 1. SH+ intervention is superior to ETAU alone in lowering the incidence of any mental disorder at 6-month follow-up.

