- 2. Refugees in the SH+ intervention arm will report an improvement in depression, anxiety and PTSD symptoms, psychosocial well-being and improved levels of psychological functioning, when compared to ETAU group.
- 3. Refugees in the SH+ intervention arm will incur lower health care costs compared to ETAU group.

STUDY DESIGN

RE-DEFINE in Turkey is a prospective, randomized, parallel-group trial that will follow study participants over a period of 12 months. Arabic speaking people including Syrians under the temporary protection of Republic of Turkey and other Arabic speaking immigrants and asylum seekers with psychological distress, but without a mental disorder according to the MINI International Neuropsychiatric Interview (M.I.N.I.) for DSM-V and ICD-10, will be randomly assigned to the SH+ intervention or to enhanced treatment as usual (ETAU). Participants, facilitators, and research staff involved in the screening and baseline assessment will not be blind to the interventions provided during the trial. Participants will be assessed at baseline before randomization, immediately post-intervention, and at 6 and 12-months of

follow-up (Appendix 6). All assessments carried out after random allocation will be performed by masked assessors. All phases of the trial will be recorded following the CONSORT statement (25;26).

METHODOLOGY

Eligibility Criteria

Inclusion criteria:

- (a) Age 18 or above;
- (b) Able to speak and understand Arabic
- (c) Being an Arabic speaking person including Syrians under the temporary protection of Republic of Turkey and other Arabic speaking immigrants and asylum seekers;
- (d) Presence of psychological distress, as shown by a score of 3 or more at the 12 item General Health Questionnaire (GHQ- $12 \ge 3$);
- (e) Both oral and written or online informed consent to enter the study.

Exclusion criteria:

- (a) Presence of any mental disorders according to DSM-V and ICD-10, as shown by a positive M.I.N.I.;
- (b) Acute medical conditions contraindicating study participation, based on clinical judgment of the trained interviewer who performs the screening;
- (c) Clinical evidence of imminent suicide risk or suicide risk scored as "moderate or high" (or a positive suicidality behaviour disorder) by the M.I.N.I. (section SUICIDALITY);
- (d) Clinical evidence that the decision-making capacity is impaired.

Box 1. Definition of asylum seekers and refugees

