Syrians who fled to Turkey as a result of the humanitarian crisis in Syria are not considered as refugees or asylum seekers in Turkey, instead they are under temporary protection according to Law on Foreigners and International Protection, and the Temporary Protection Regulation. Because, Turkey signed the 1951 Geneva Convention with an additional condition. This condition involves a geographical limitation which only allows people who arrive from the west of Turkey to be liable to asylum procedures. Therefore, Syrians who seek international protection are not able to become refugees or asylum seekers in Turkey. The Directorate General for Migration Management (DGMM) is responsible for registration and verification of Syrians with regard to the Law on Foreigners and International Protection, and the Temporary Protection Regulation. Temporary protection allows Syrians to access public services (27). Throughout this protocol, Syrians under temporary protection may be referred as Syrian refugees in order to be in accordance with European study protocol of RE-DEFINE: SH+.

Setting

The study will be conducted in Turkey. A detailed description of the setting and the recruiting process is reported in Appendix 1. The recruitment strategy will be pragmatic and will involve local organizations, namely non-governmental organizations (NGOs), that are not only in Istanbul but in other cities of Turkey as well where refugees reside, and implement reception projects for refugees in Turkey. These non-governmental organizations should undertake integrated reception interventions that include food, housing, legal, educational, healthcare and social guidance and support, and the development of individual programmes to promote socioeconomic inclusion and integration. In the recruiting site, local organizations that comply with the criteria will be contacted and the RE-DEFINE project will be presented as a possibility

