The member of the research team will have no responsibility in checking that refugees actually follow the suggested clinical pathway. Psychiatric care costs will be covered in accordance with the local healthcare system. Given the limited services and transient nature of some refugees in Turkey, it will not be possible for the research team to always check if Syrian refugees actually follow the suggested clinical pathway. Local healthcare systems will cover psychiatric care costs. An SOP will define in detail how the referral to mental health care services will be conducted.

Trial phase *Pilot phase*

Before starting the study we will conduct a preliminary pilot phase with 3-4 participants for each site. This phase will allow testing different aspects related to the delivery of the intervention and assessments, feasibility, and time, prior to the performance of the trial. Participants of the pilot study will not be included in the final sample size. However, they will receive the experimental condition, and a close monitoring of their psychological status through two psychological assessments (one at baseline, and one at the end of the intervention). These assessments will be composed of the same instruments that will be used in the fully-powered trial.

Trial phase assessment

Assessments will take place at screening, at baseline (before random allocation), post-intervention (0-1 week after intervention), and at 6- and 12- months after randomization. The assessments at 6- and 12- months will be performed in person or by telephone/videoconferencing, to ensure the required rates of follow up. Telephone or online assessment and counselling has been used in a range of studies, with a critical review concluding that findings to date are positive and online counselling can have a similar impact and replicate the therapeutic conditions found in face-to-face encounters¹. In addition, a previous study has shown that a mixture of online and telephone based assessments for inclusion in a remote writing based intervention for Post Traumatic Stress Disorder (PTSD) can be feasibly implemented with war traumatised individuals in Iraq². This approach is continuing to be used widely (http://ilajnafsy.bzfo.de/portal/en/)

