Psychological distress (GHQ-12); number of participants with a psychiatric diagnosis at post-intervention and at 12-month follow-up (M.I.N.I.), functioning (WHODAS 2.0), depressive symptoms (PHQ-9), subjective wellbeing (WHO-5 Wellbeing Index), self-defined psychosocial goals (PSYCHLOPS), health related quality of life (EQ-5D-3L), symptoms of PTSD (PCL-5), drop-out rates due to any reason, cost-effectiveness (CSSRI-TR adapted).

Psychological distress

General Health Questionnaire-12 (GHQ-12) (35). The GHQ-12 is a measure of current mental health developed by Goldberg in the 1970s, and it has been extensively used in different settings and cultures (36-38). The questionnaire asks whether the respondent has experienced a particular symptom or behaviour recently. Each item is rated on a four-point Likert scale (less than usual, no more than usual, rather more than usual, or much more than usual); and gives a total score of 36 or 12 based on the GHQ version and on the selected scoring methods. The most common scoring methods are bi-modal (0-0-1-1) for screening and Likert scoring styles (0-1-2-3) for outcome evaluation.

Psychiatric diagnosis at post-intervention and at 12-month follow-up

The M.I.N.I. interview will be administered also at post-intervention and at 12-month follow-up, to evaluate the presence of any mental disorders.

Functioning

The WHO Disability Assessment Schedule 2.0 (WHODAS) interviewer-administered version (39;40). The WHODAS is a generic assessment instrument assessing health and disability (39). It is used across all diseases, including mental, neurological and substance use disorders. It is simple to administer and applicable across cultures. WHODAS covers six domains (cognition, mobility, self-care, getting along, life activities, and participation). It assesses difficulties people have across these domains during the last 30 days. Difficulties are scored as none, mild, moderate, severe, or extreme. We will use the 12-item interviewer-administered version. Data on socio-demographic information (sex, age, education, marital status and work status) will be collected through questions A1-A5 of the WHO-DAS, which will be administered first (39;40).

Depressive symptoms

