Proportion of participants leaving the study early (dropouts)

Number of people leaving the study prematurely at any times, and reasons for discontinuation. If possible, this information will be collected in person, or by telephone or secure online audio/video communication (two attempts will be made to reach participants). Unreachability of participants will also be recorded as a dropout.

Cost-effectiveness measures

The Client Service Receipt Inventory (CSSRI): Client sociodemographic and service receipt inventory (adapted version with other socio-demographic characteristics). The CSSRI is a research tool developed for collecting information that describes in detail the types and level of services that comprise the care package of each study member (46). These data are important in their own right as they can inform decisions about planning, commissioning and providing services to meet the needs of particular populations. However, the schedule is designed so that service use data are recorded in a standardized way that best facilitates the estimation of the component and total costs of support for each client. Just as needs or outcome data are collected at the individual level, in an economic evaluation it is important to measure the costs of the resources used to generate those outcomes for each client. The CSSRI is a questionnaire which takes approximately 20 minutes to complete and collects retrospective information about the interviewee's use of health and social care services, accommodation and living situations, income, employment and benefits. The CSSRI-EU is a European version of the CSRI. The CSSRI-EU was developed within the framework of the EPSILON (European Psychiatric Services: Inputs Linked to Outcome Domains and Needs) project. It will be further adapted to include relevant information for Turkey. The instrument is applicable for use in interview with patients and/or key staff.

For the purposes of RE-DEFINE, the European version of the CSSRI will be adapted to be used with refugees. This will be completed by sending the questionnaire to experts and local providers for comments on the questionnaire.

Traumatic life events and adverse life events

Traumatic/adverse life events and daily and environmental stressors will be collected by administering the HTQ-Part A and the 17-item Checklist for Post-Migration Living Difficulties (PMLD).

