After the last data lock, a mixed analysis of covariance (ANCOVA) will be performed for each scale, using the values at post-intervention, and at 6- and 12- months of follow-up, controlling for the value at baseline. In case of joint statistical significance of the coefficients related to treatment status, the analysis for each outcome/time combination will be repeated using the last observation carried forward (LOCF) approach: ratings will be carried forward from the last available assessment to the 12-month follow-up assessment. Multivariate analyses will be performed for each scale to take confounding factors into account, again including the baseline value as a covariate.

Proportion of participants leaving the study early (dropouts)

The proportion of participants leaving the study early will be compared between the two groups through the chi-square test (or the Fisher exact test, where appropriate). A multivariate analysis will be performed through a Poisson regression model, with a robust error variance, to estimate relative risks directly and to explore the potential confounding effect of prognostic factors, and the interactions with treatment (57).

Cost-effectiveness analysis (CSSRI)

Overall incremental cost-effectiveness analyses (ICEA) will be conducted from the UK health and social care system perspective and from the UK societal perspective by means of the netbenefit approach (Glick, 2010). Direct costs including formal medical and psychiatric health care (inpatient care, outpatient care, staff, equipment, drugs; formal psychological), psychosocial care (psychological counselling, psychotherapy, social worker, community nurse, sheltered accommodation, day centre, occupational services), legal services (police and court contacts, arrests, legal guardianship), informal services (care provided by relatives or volunteers) will be used for ICEA from the health and social care system (payer) perspective and total (direct costs + productivity losses) will be used for ICEA from the societal perspective.

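### The economic question is about Turkey, but the analysis is fixed to UK perspectives and UK unit costs

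*Protocol*

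**What the plan says.** The economic question is set in Turkey throughout the early sections of the protocol:

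- The Background of the Project Summary gives as the evidence gap that "there is no rigorous evidence on its cost-effectiveness in preventing the onset of mental disorders in refugees in Turkey".
- The Rationale closes by saying that "this study will evaluate the cost-effectiveness of SH+ in Turkey". The Objectives section ties the cost-effectiveness aim to refugees resettled in Turkey.
- Hypothesis 3 reads "Refugees in the SH+ intervention arm will incur lower health care costs compared to ETAU group".
- Under Setting: "The study will be conducted in Turkey".
- In the referral text of the Screening phase: "Local healthcare systems will cover psychiatric care costs".
- Under Cost-effectiveness measures, the service-use inventory is described with the words "It will be further adapted to include relevant information for Turkey". The Secondary outcomes section calls it CSSRI-TR.

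The section Cost-effectiveness analysis (CSSRI) then says that the incremental analyses "will be conducted from the UK health and social care system perspective and from the UK societal perspective". Unit costs come from a compilation for the UK system, and other price sources are allowed only for services missing from it. All costs are in 2017 pounds. The willingness-to-pay range is UK£ 0 to 50,000 in steps of 5,000. Results are interpreted by NICE thresholds and, alternatively, by country-specific ones.

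**The concern.** The perspective of an economic evaluation determines whose costs count, and the unit-cost source determines what they are worth. Here both belong to a country in which the trial does not take place. A Turkish decision-maker reading the result would learn whether SH+ represents value to a UK payer or to UK society, given service use observed in Turkey.

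This is not detail left for a statistical analysis plan. The protocol fixes a perspective and a price source, and both conflict with its own objective. At stake are the ICER, the net monetary benefit, the acceptability curve and, because it rests on costs valued in the same way, the cost comparison in hypothesis 3. The primary outcome is not touched.

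**Working it through.** The protocol gives no expected cost, QALY gain or ICER, so there is no planned figure to reproduce. The check compares the texts and then follows the planned formulas.

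**Step 1. Question against analysis.**

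| Element | Stated question or setting | Planned analysis |
|---|---|---|
| Jurisdiction | Turkey | UK |
| Service use | Collected in Turkey, inventory adapted for Turkey | Same data |
| Unit costs | Not stated for Turkey | UK compilation; other sources only for unlisted services |
| Currency and year | Not stated for Turkey | 2017 pounds |
| Threshold | Not stated | NICE; alternatively country-specific |
| Utilities, salaries | Not stated | Country-specific utilities and group-average salaries, no country named |
| SH+ delivery | Included in total costs | No price source named |

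The conflict lies in the perspective and the unit-cost source. The text does not tie every input to the UK.

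**Step 2. Where prices enter.** The cost section multiplies service units by unit costs to give each participant's cost C. Then:

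- ICER = ΔC / ΔQ
- NMB = QALY × MWTP − C, so incremental NMB = MWTP × ΔQ − ΔC
- the acceptability curve is built from the NMB over (50,000 − 0)/5,000 + 1 = 11 grid points

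All three use the same C, so all three inherit the UK prices.

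**Step 3. One common price ratio.** Suppose every Turkish price is c times the UK price. Then ΔC becomes cΔC. Its sign is unchanged, and a positive ICER of X becomes cX. Assumed illustration (not from the protocol): ΔQ = 0.01, ΔC = £100 at UK prices, MWTP = £20,000.

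| c | ICER | Incremental NMB |
|---|---|---|
| 1 | 100/0.01 = £10,000 | 200 − 100 = £100 |
| 0.5 | 50/0.01 = £5,000 | 200 − 50 = £150 |
| 2 | 200/0.01 = £20,000 | 200 − 200 = £0 |

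**Step 4. Thresholds.** Let T be the UK threshold and T′ the Turkish one. Comparing X with T answers a UK question. Comparing X with T′, the planned alternative, sets UK-priced costs against a local threshold. The Turkish answer compares cX with T′, which is not planned. The planned alternative gives a different decision from the Turkish one whenever T′ lies between X and cX.

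**Step 5. Different price ratios.** Let D be delivery cost and S the value of averted services, both at UK prices. Let b and a be the Turkish/UK price ratios for delivery and services. Then ΔC in Turkey = bD − aS. Assumed illustration: D = £300, S = £200, so ΔC = +£100 at UK prices.

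- b = 0.25, a = 0.10: 75 − 20 = +£55
- b = 0.10, a = 0.25: 30 − 50 = −£20, so SH+ becomes cost-saving

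The sign changes when a/b passes D/S = 300/200 = 1.5. Converting currency cannot correct this, because the relative prices differ. If delivery were already priced locally under the plan, set b = 1: the Turkish difference is D − aS, and even a common price level would no longer protect the sign. The protocol gives neither a nor b.

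**The case against.** The best case for the plan has five parts.

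*The UK frame may harmonise this trial with its European counterpart.* Box 1 mentions a European RE-DEFINE protocol, but only to explain the use of the word refugee. The cost section offers no such reason. If one exists, it supports a secondary UK analysis and does not replace a Turkish one.

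*The plan has local content.* Utilities are country-specific, unlisted services may be priced elsewhere, a country-specific threshold is an alternative, and regression cost functions will examine macroeconomic and health care indicators. This stands as a limit on the criticism, but none of it supplies a Turkish perspective or Turkish prices for the listed services.

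*The statement that local systems pay is narrower than it looks.* It covers psychiatric care and sits in the referral text for people excluded at screening. The control-intervention section extends referral to participants who later develop a disorder. It does not show who pays for legal services, accommodation or informal care, which are also costed. This stands, so that sentence is supporting evidence only.

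*The effect may be small.* Under a common price ratio the sign of the cost difference survives, so hypothesis 3 could still be answered in direction. If T′/T = c, the UK and Turkish decisions agree. Both are correct, but nothing in the documents shows that either condition holds.

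*Turkish unit costs may be hard to obtain.* The documents are silent on this, so the effort cannot be judged from them.

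**Conclusion.** The concern holds with high confidence, because it rests on the protocol's own text: a Turkish question, and an analysis fixed to UK perspectives and a UK unit-cost source without a stated reason. Size and direction cannot be determined. The price ratios, cost differences and QALY gain used above are assumptions that show the mechanism, and no claim is made that UK prices favour or penalise SH+.

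This should be fixed, but it does not threaten the trial. It concerns a secondary objective, the data collected remain usable, and the primary outcome is unaffected.

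**What to change.** In Cost-effectiveness analysis (CSSRI):

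1. Make the Turkish health and social care (payer) perspective and the Turkish societal perspective the base case.
2. Name a Turkish unit-cost source, and use Turkish wages for informal care and productivity losses.
3. Value SH+ delivery on the same price basis, and state the currency and price year.
4. Interpret the base case against the country-specific threshold, naming Turkey, and restate the willingness-to-pay range to match. Test hypothesis 3 on these costs.
5. Keep the UK-priced analysis, if wanted, as a labelled secondary analysis with its reason stated.

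Because costs are units times unit costs, the service use already collected can be re-priced. No new participant data and no change to the CSSRI schedule are needed. The cost is assembling Turkish unit costs for the listed services, which the protocol does not now plan. The effort depends on sources the documents do not describe, and the work can precede the analyses timetabled for months 28 to 36 in Duration of the project.
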